8.3 Crossover Between Study Arms

If a participant has or develops a contraindication to the specific drug they have been randomized to receive prior to discharge on EP (ie prior to initiation of the study intervention), they will be considered for crossover to the other arm and, if there is no contraindication to the other drug, can be switched to that arm. These instances and reasons for crossover will be documented. Crossover in this way will be allowed so that patients are not deprived of the standard of care anticoagulation after RC for their participation in the study and to better mimic the current prescribing patterns in which the drugs are frequently substituted for each other. Potential bias from allowing crossover is expected to be minimal as there is not a strongly plausible link between the contraindications to enoxaparin or apixaban and adherence to enoxaparin or apixaban. Furthermore, the contraindications to enoxaparin and apixaban are mostly quite rare; the only anticipated contraindication will be creatinine clearance (CrCl) <30 for enoxaparin. Any other possible indication for crossover will be reviewed by PI. Patients who crossover should still complete the study visits and both an intention to treat (ITT) and perprotocol (PP) analyses will be completed.

9 STATISTICAL CONSIDERATIONS

9.1 General Approach

Continuous variables will be presented as means with standard deviation or median with interquartile range. All statistical tests of significance will be two-sided with alpha level 0.05. Stata will be used for all statistical analysis.

9.2 Baseline Descriptive Statistics

Participants in the two study arms will be compared on their baseline demographics characteristics, collected from the Demographics Questionnaire, and on their operative characteristics, collected by chart review. Inferential statistics will be used to test for significant differences across study arms at baseline. To conduct these statistical tests, we will apply either standard t-tests for continuous measures or difference in proportion tests for binary measures.

9.3 Analysis of the Primary Endpoint

The primary objective of this study is to compare drug adherence between the two study arms, and the corresponding primary endpoint of the study is the proportion of days at home during which the participant took the prescribed anticoagulant. This is defined as the proportion of days covered (PDC).

PDC = number of days of anticoagulant actually taken / number of days of anticoagulant supposed to take

Number of days of anticoagulant actually taken is determined during the POD 30 phone call by asking the participant how many pills/vials they have remaining and then subtracting that from the size of the prescription they were given. Number of days of anticoagulant supposed to take is calculated by subtracting the number of days postop the patient was discharged from 30.

PDC will be compared between the two groups using a **non-inferiority trial design** with difference in proportions test with the following hypothesis:

H₀: Apixaban is inferior to Enoxaparin in terms of the average PDC response.

HA: Apixaban is non-inferior to Enoxaparin in terms of the average PDC response.

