1.1 Synopsis

Title: Comparison of Apixaban versus Enoxaparin for VTE Prevention after

Radical Cystectomy (the CARE trial)

Short Title: Comparison of Apixaban versus Enoxaparin (CARE)

Study Description:

Patients who have undergone radical cystectomy for bladder cancer will be randomized to receive a prescription for either enoxaparin or apixaban to self-administer at home until post operative day 30. Their adherence to the assigned medication will be the primary outcome. Comparisons of patient satisfaction, barriers to adherence, and cost will also be collected. The hypothesis is that adherence, satisfaction, and cost will be greater in the apixaban arm.

Objectives:

1. To compare rates of adherence to discharge on enoxaparin vs apixaban

a. Hypothesis: The apixaban group will exhibit non-inferior adherence, as measured by the proportion of prescribed medication accurately administered.

2. To compare costs of discharge on enoxaparin vs apixaban

a. Hypothesis: The median patient out-of-pocket cost, obtained from the institution's outpatient pharmacy data, is expected to be higher in the apixaban group compared to enoxaparin group.

3. To explore factors contributing to EP adherence

a. Hypothesis: it is anticipated that barriers to adherence to enoxaparin will primarily manifest as operational challenges and patient dissatisfaction, while for apixaban, they will predominantly arise from lack of insurance coverage and cost considerations. To evaluate these barriers, a combination of validated questionnaires and novel measures will be employed.

4. To collect safety and efficacy data on enoxaparin and apixaban

a. Considering that our study size will limit statistical power to detect risk reduction in venous thromboembolism (VTE) and/or bleeding events in either enoxaparin or apixaban, we will instead closely monitor and assess VTE and bleeding events in both treatment arms to contribute to existing studies for possible meta-analysis. This will be achieved

through the implementation of screening questions at each visit.

Primary Endpoint:

To address our primary objective, adherence, the primary endpoint will be measured as the proportion of days covered (PDC), ie the proportion of days between discharge and post operative day 30 during which the participant took their anticoagulant as prescribed.

Secondary Endpoints:

To address our secondary objective of comparing risk factors for adherence/non-adherence, secondary endpoints include:

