6 STUDY INTERVENTION

Both enoxaparin and apixaban are FDA approved in the setting of VTE prophylaxis and considered standard of care for EP after radical cystectomy. Study personnel will not be directly providing or administering either drug. Rather, the study intervention is the randomization to receive a prescription (with standard clinical counseling) for either of the two forms of prophylaxis. The participant will then be responsible for filling the prescription at their own cost and self-administering the anticoagulant, as would be standard of care after a radical cystectomy. The anticoagulants will be prescribed according to the clinical standard of care: 40 mg injected subcutaneously once daily for enoxaparin and 2.5 mg tablet taken orally twice daily for apixaban. Doses may be reduced in increased based on the patient's medical comorbidity profile (for example weight and CrCl) according to standard prescribing practices. Regardless of the time of day of discharge, participants will be instructed to start self-administering the medication the day after discharge, and continue through post-op day 30.

Participants who fail to receive a prescription for either anticoagulant will be considered not to have received the study intervention. Participants who receive the prescription but report poor compliance with the prescription have still received the study intervention; their poor compliance is tracked as the primary outcome of the study.

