7.1 Adherence & Satisfaction Assessments

The following assessments will be made to assess the adherence and satisfaction with anticoagulants after cystectomy (corresponding to primary and secondary objectives in section 3):

- 1. Medication counting—study personnel will assist with medication counting over the phone. This involves the participant counting the pills/vials of medication they have remaining and then the study personnel will use the date of surgery, date of discharge, and size of prescription found in the medical record to calculate the **proportion of days covered (PDC)**. PDC is the primary endpoint of the study and is the most objective measure of adherence.
- 2. National Institute of Health (NIH) Patient-Reported Outcomes Measurement Information System (PROMIS) Medication Adherence Scale (PMAS)^{29,30} this questionnaire is a validated, nine-item, patient-reported measure of medication adherence that can be either administered by study personnel over the phone or filled out directly in RedCap by study participants who elect to have a secure weblink emailed to them.
- **3.** Patient Satisfaction study personnel will ask a series of independent questions over the phone or participants will answer them directly in RedCap if they elect to have a secure weblink emailed to them. These questions elucidate possible reasons for compliance/noncompliance that are hypothesized specifically to apply to enoxaparin and apixaban.

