9.5 Exploratory Analysis

Analysis of other factors influencing adherence to at home anticoagulation in this population are considered exploratory. To explore what factors other than type of anticoagulant may be impacting adherence, we plan to perform a logistic regression with the outcome variable of PDC. Covariates will include the following: age, gender, ethnicity, marital status, living situation, occupational status, education level, annual household income, insurance status, history of prior blood clot, number of daily medications, discharge destination, study arm, and items from the Satisfaction Questionnaire. Univariate regression will be performed first followed by multivariate regression including all variables that were significantly associated on univariate regression.

A second exploratory analysis will be comparing elements of the novel satisfaction questionnaire trial between the apixaban and enoxaparin arms. Items from this questionnaire may be compared by presenting descriptive statistics without formal tests for statistical significance in order to explore how patient satisfaction varies between the study arms and allow future physicians to give anticipatory guidance.

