10.4 Adverse Events

The medical complication rate after radical cystectomy is relatively high; it has been reported around 60% for all complications and 30% for Common Terminology Criteria for Adverse Events (CTCAE) Grade 3 complications in the first 90 days postoperatively. ³⁷ Therefore the vast majority of adverse events in this study are expected and have no plausible relation to VTE prophylaxis with either enoxaparin or apixaban. The known risks of enoxaparin and lovenox are defined on the drug labels

The study goal is to evaluate VTE and bleeding events. These will be specifically and directly solicited from participants at the study visits as a well as screened for in patients who do not directly report events. Patients will be referred to their treating provider for management. See section 7.4 for further detail on the screening for and management of VTE and bleeding events.

Additional adverse events will be screened for during telephone calls at POD 30 and POD 90. The AE assessment period will start when participants are discharged as this coincides with

the start of the study intervention. Adverse events are classified as serious or non-serious. A serious adverse event is any AE that, in the view of the investigator, is:

- fatal
- life-threatening
- requires or prolongs hospital stay
- results in persistent or significant disability or incapacity

SAEs discovered in telephone calls will be immediately referred to a study investigator, who will review the event, possibly contact the participant to ensure they are referred to an appropriate level of immediate management, and notify the participant's treating clinician for any further management. The SAE form will be completed, including start and stop date, description, and grade according to the CTCAE version 5 (full guideline:

https://ctep.cancer.gov/protocoldevelopment/electronic_applications/docs/CTCAE_v5_Quick_R eference 8.5x11.pdf):

Grade 1 Mild; asymptomatic or mild symptoms; clinical or diagnostic observations only; intervention not indicated.

Grade 2 Moderate; minimal, local or noninvasive intervention indicated; limiting age appropriate instrumental ADL.

Grade 3 Severe or medically significant but not immediately life-threatening; hospitalization or prolongation of hospitalization indicated; disabling; limiting self care ADL.

Grade 4 Life-threatening consequences; urgent intervention indicated.

Grade 5 Death related to AE.

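### The adherence formula in 9.3 keeps readmission days in the denominator but counts only home-supply doses, so days dosed from hospital stock would be scored as missed

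*Combined protocol and SAP*

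**What the plan says.** The endpoint is worded in two ways. Section 9.3 calls it the "proportion of days at home during which the participant took the prescribed anticoagulant". The synopsis (1.1) calls it "the proportion of days between discharge and post operative day 30 during which the participant took their anticoagulant as prescribed".

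The formula in 9.3 is days taken over days due. Days due are "calculated by subtracting the number of days postop the patient was discharged from 30". Days taken come from "asking the participant how many pills/vials they have remaining and then subtracting that from the size of the prescription they were given". Section 7.1 names the other inputs: "study personnel will use the date of surgery, date of discharge, and size of prescription found in the medical record". Readmission dates and source of supply are not among them.

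The denominator fits the dosing window in Section 6, where participants are told to "start self-administering the medication the day after discharge, and continue through post-op day 30".

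Section 9.4 adds a binary measure that requires every intended dose, and 9.7 uses that classification to define a second safety population. Discharge destination appears only in the exploratory covariate list in 9.5 ("number of daily medications, discharge destination, study arm"), so discharge to a facility is foreseen and not excluded. Section 10.4 cites "30% for Common Terminology Criteria for Adverse Events (CTCAE) Grade 3 complications in the first 90 days postoperatively". No readmission rate or length of stay is given anywhere.

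**The concern.** The numerator sees only doses drawn from the discharge prescription. The denominator runs over all days to POD30, wherever the participant was. On a readmission day covered by hospital stock, the home count does not fall, but the day stays in the denominator.

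That score is wrong under either wording. If the endpoint is days at home, the day should not be in the denominator. If it is all days from discharge to POD30, the anticoagulant was taken and the day should be in the numerator.

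What is at stake is a primary endpoint that partly measures readmission instead of adherence. Loss of credit that is common to both arms shrinks any true difference, which in a non-inferiority comparison favours the conclusion of non-inferiority. Loss that differs by arm, for example through bleeding admissions, biases the difference directly. The binary measure is more fragile, because one uncredited day is enough to fail it.

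**Working it through.** The plan gives no figure for readmission or its effect, so there is none to reproduce. The check follows the formula as written.

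**Inputs from the documents:** denominator D = 30 − discharge day (9.3); latest discharge POD14 (5.2), so D is at least 16; control PDC (proportion of days covered) 85%, margin 15 points, 45 per arm, one-sided 0.05 (9.3.1).

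**Assumptions:** L readmission days, all dosed from hospital stock; a proportion r readmitted, 10% to 30%; L from 3 to 7; discharge on POD7, so D = 23; readmission unrelated to adherence on other days.

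**One participant who takes every home dose.** Written formula: (D − L)/D. With the L days removed from the denominator: (D − L)/(D − L) = 100%.

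| Discharge | D | L = 3 | L = 5 | L = 7 |
|---|---|---|---|---|
| POD7 | 23 | 20/23 = 87.0% | 18/23 = 78.3% | 16/23 = 69.6% |
| POD14 | 16 | 13/16 = 81.2% | 11/16 = 68.8% | 9/16 = 56.2% |

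**Equal readmission in both arms.** Each arm's mean is multiplied by f = 1 − rL/D, so a true 15-point deficit appears as 15f.

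| r, L | f | Apparent deficit |
|---|---|---|
| 10%, 3 days | 1 − 0.3/23 = 0.987 | 14.8 points |
| 20%, 5 days | 1 − 1.0/23 = 0.957 | 14.3 points |
| 30%, 7 days | 1 − 2.1/23 = 0.909 | 13.6 points |

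**Effect on the one-sided error at the margin.** This is Φ(−1.645 + (0.15 − 0.15f)/SE). The SE uses 45 per arm and includes the variance that readmission adds. The plan states no SD for PDC, so I took 0.168 to 0.285. In the mildest scenario with SD 0.285, SE = 0.0597 and the error is about 5.4%. In the most extreme with SD 0.168, SE = 0.0398, the shift is 0.0137/0.0398 = 0.34, and the error is about 9.7%. With SD 0.285 the extreme scenario gives about 7.8%.

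**Unequal readmission.** A 10-point imbalance shifts the difference by 0.10 × L/D: 0.3/23 = 1.3 points for 3 days, 0.5/23 = 2.2 for 5 days and 0.7/23 = 3.0 for 7 days, if all other days are fully covered. At 85% coverage on other days, the 3-day and 7-day figures become 1.1 and 2.6.

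**The case against.** The strongest reply is that the synopsis definition and the Section 6 dosing window both match the 9.3 denominator, and that at home may simply be loose wording for after discharge. On that view there is only a wording inconsistency, and a fixed window is a legitimate estimand. The point about the denominator stands. It does not rescue the numerator, because a dose given from hospital stock is a dose taken and the count still misses it.

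Several stronger readings are tempting, and the documents do not support them:

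- **That a readmitted participant is scored as non-adherent on the primary endpoint.** PDC is continuous, so credit is lost in proportion to days away. The label applies only to the binary measure in 9.4, and only if that is judged from the same count, which 9.4 does not say.
- **That facility stays have the same problem.** The documents do not say whose supply is used there. If it is the participant's own filled prescription, the count falls normally and nothing is lost.
- **That the fall in mean PDC can be set against the 15-point margin.** The fall is within an arm (up to 2.1/23 = 9.1 points in the extreme scenario), while the margin concerns the difference between arms.
- **That the 30% figure in 10.4 is a readmission rate.** It counts grade 3 complications over 90 days from surgery.

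It is also fair to say that equal readmission leaves the difference unbiased when the arms are truly equal. It does not do so at the margin, where the non-inferiority error is defined. Finally, removing readmission days makes the denominator depend on something that happens after randomisation. That is a real cost and the reason to keep the fixed-window version.

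**Conclusion.** The concern holds in a limited form. The wording and formula in 9.3 disagree, the synopsis words the endpoint differently again, and no rule covers readmission. Where hospital stock is used, the formula gives a wrong score under either wording.

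For an individual the error can be large: 78% instead of 100% in the POD7, 5-day example. For the comparison it is modest. With equal readmission, a true 15-point deficit is attenuated by about 0.2 to 1.4 points, in the anti-conservative direction. The one-sided error approaches 10% only in the most extreme scenario with the smaller SD. A 10-point imbalance in readmission moves the difference by about 1.3 to 3.0 points.

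All of these sizes rest on the assumed readmission rates, lengths of stay, 23-day window and hospital supply. The mismatch itself rests on the text alone. It is worth correcting because it concerns the primary endpoint, the correction is cheap, and in an open-label trial the scoring rule should be fixed before analysis.

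**What to change.** 1. Use one definition of the endpoint in the synopsis, Section 3, Section 7.1 and Section 9.3.
2. At the POD30 call and from the chart, record readmission dates within the window and the source of the anticoagulant supply on those days.
3. In 9.3, remove from the denominator the inpatient readmission days not dosed from the home supply, or alternatively credit documented inpatient doses in the numerator. Choose one rule now.
4. Apply the same rule to the binary measure in 9.4, and so to the adherent safety population in 9.7.
5. Keep the present fixed-window PDC as a sensitivity analysis.
6. Do not subtract all facility days. A participant in a facility through POD30 would have a zero denominator and drop out of the intention-to-treat set. Keep facility discharges in the primary analysis and add a sensitivity analysis that excludes them.

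The cost is a wording change and one or two data fields. The POD30 call already screens for adverse events, including those that require a hospital stay, and charts are already reviewed, but Sections 7.1 and 7.3 do not list readmission dates or source of supply. The remaining downside is the post-randomisation denominator, which the fixed-window sensitivity analysis addresses.

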3 STUDY OBJECTIVES AND ENDPOINTS

OBJECTIVES	ENDPOINTS	JUSTIFICATION FOR ENDPOINTS
Primary		
To compare rates of adherence to discharge on enoxaparin vs apixaban	Proportion of days covered (PDC). This will be calculated based on the size of prescription the patient was provided, day of surgery, day of discharge, and how many pills/syringes are remaining at POD30.	This is an objective and quantitative way to measure adherence.
Secondary		
To explore possible reasons for adherence vs non adherence	PROMIS Medication Adherence Scale: a nine-item questionnaire ^{26,27}	This is a validated measure of medication adherence that focuses on the possible reasons for non-adherence
	Participant satisfaction	Participants will answer questions specific to the use of enoxaparin and apixaban at home after RC. These questions were selected based on the clinical experience of the PIs as well as other studies that have examined adherence to enoxaparin and apixaban ^{21,27,28}
	COST-FACIT: a 12-item questionnaire ²	This is a questionnaire that was developed and validated in the cancer population for assessing patient-reported financial distress due to healthcare costs. This questionnaire adds a patient reported component, as simple cost data does not capture how burdensome that cost is to each specific patient
To compare the cost of enoxaparin vs apixaban	Out of pocket cost of prescription for anticoagulant, in dollars	This provides objective measure of the cost comparison between enoxaparin and apixaban. This data combined with adherence data may allow providers to determine the most cost effective option.

OBJECTIVES	ENDPOINTS	JUSTIFICATION FOR ENDPOINTS
Tertiary		
To collect mefficacy and safety data regarding both forms of prophylaxis	Rate of VTE, either PE or DVT Rate of bleeding events, classified as major, clinically relevant nonmajor, or nonmajor.	While data suggest VTE rates are comparable between enoxaparin and apixaban in both non-urologic and urologic studies, the urologic studies are in small populations. We therefore plan to track VTE and bleeding as outcomes to continue contributing to the pool of data. These outcomes would likely have been measured even if they were not outcomes as part of safety monitoring.

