7.2 Cost Assessments

The following assessments will be made to assess the cost of anticoagulants when used as EP (corresponding to secondary objectives in section 3).

- 1. **COST-FACIT** this is a 12-item questionnaire developed and validated in the cancer population for assessing patient-reported financial distress due to healthcare costs that can be either administered by study personnel over the phone or filled out directly in RedCap by study participants who elect to have a secure weblink emailed to them.
- 2. The total cost, amount paid by insurance, and patient out of pocket cost for each anticoagulant (in dollars) will be tracked by the inpatient pharmacy. This is collected via electronic review of pharmacy records.

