8.2 Discontinuation of Study Intervention, Discontinuation from Study

Prophylactic anticoagulation is standard of care after RC and therefore the decision to stop prophylaxis should be situated within a discussion with the treating clinician. The following are anticipated reasons participants may be told to discontinue study intervention (ie stop their anticoagulant) by their treating clinician:

- Development of blood clot. This would require discontinuation of prophylactic dose in favor of therapeutic dose and may involve switching anticoagulant type
- Development of bleeding event
- Development of an adverse event possibly related to the anticoagulant

- Development of a serious adverse event that would make prophylactic anticoagulation contraindicated

If study personnel discover any of these occurrences during study visits and they are not known already to the treating clinician, study personnel will refer the participant to their treating clinician for management, which may include consideration of discontinuation of the anticoagulant.

Study personnel will screen for discontinuation of the study intervention (ie discontinuation of the assigned anticoagulant) that has already occurred at the beginning of the POD30 and POD90 telephone calls. Any instances of study discontinuation will be brought to the attention of the PI and at the discretion of the PI participants who must discontinue the study intervention may remain in the study and complete portions of study visits depending on their reason for anticoagulant discontinuation and length of time they were following study protocol.

Participants may alternatively be discontinued completely from the study for the following reasons:

- Failure to undergo radical cystectomy and pelvic lymph node dissection
- Failure to be discharged on prophylactic anticoagulant
- Failure to be discharged by POD14
- Lost to Follow Up, defined as failing to complete the study visit despite three attempts to contact the participant via phone and/or email
- Participant request; participants are free to withdraw at any time

Any study discontinuation or discontinuation of the study intervention will be documented, including the date and reason for discontinuation. All instances will be reviewed by PI.. Participants who are discontinued will not be replaced.

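### The PDC count in section 9.3 credits drug that was prescribed but never obtained, so a participant who never fills the script can score 100% or more on the primary endpoint

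*Combined protocol and SAP*

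**What the plan says.** Section 9.3 defines the primary endpoint as "PDC = number of days of anticoagulant actually taken / number of days of anticoagulant supposed to take". It obtains the numerator by "asking the participant how many pills/vials they have remaining and then subtracting that from the size of the prescription they were given", and the denominator as 30 minus the postoperative day of discharge. Section 7.1 names the source of the starting quantity: staff "use the date of surgery, date of discharge, and size of prescription found in the medical record". The endpoint table in section 3 lists the same inputs: "size of prescription the patient was provided, day of surgery, day of discharge, and how many pills/syringes are remaining at POD30". The quantity obtained from a pharmacy is not among them.

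Section 6 says that study staff supply no drug: "The participant will then be responsible for filling the prescription at their own cost". Section 5.2 excludes people who receive no script, not people who do not fill one. Section 6 also keeps the latter in the primary outcome: "Participants who receive the prescription but report poor compliance with the prescription have still received the study intervention".

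Two other procedures could bring a non-fill to light. In section 8.2, "Study personnel will screen for discontinuation of the study intervention (ie discontinuation of the assigned anticoagulant) that has already occurred" at each call. In section 7.2, pharmacy records are reviewed for cost, including "amount paid by insurance, and patient out of pocket cost for each anticoagulant (in dollars"). Neither is linked to PDC. No section scores a non-filler as 0 or caps PDC at 1.

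**The concern.** The subtraction measures drug taken only if the starting quantity is what the participant had in hand. Here it is what was prescribed. Someone who never filled the script has zero units remaining and is recorded as having taken all of it. The unfilled part of a partly filled script is credited in the same way. The count then contradicts the definition it is meant to measure, and complete non-adherence can enter the primary analysis as complete adherence.

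The protocol itself treats access as a real barrier. The Synopsis expects coverage and cost problems with apixaban. Section 2.1 reports coverage problems (38%), affordability problems (51%) and refusal of injections (about 20%) with enoxaparin. Table 2 shows prior authorizations denied for 9 of 41 apixaban and 2 of 21 enoxaparin requests. Denials are not non-fills, but they show how a non-fill can arise.

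Three results are exposed:
- the arm means and the non-inferiority comparison;
- the section 9.5 regression of PDC on income and insurance status, where a participant who could not afford the drug would appear fully adherent;
- if the section 9.4 adherent category is derived from the same count, the adherent safety set in section 9.7, which would include people who took no drug.

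**Working it through.** The plan states no PDC value for a non-filler, so there is no figure to reproduce. The check applies the section 9.3 rule directly, with units converted to days.

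**Inputs from the documents:** days due = 30 − D, where D is the discharge day (9.3); D at most 14 (5.2); 45 per arm, control PDC 85%, margin 15 points, 80% power, one-sided 0.05 (9.3.1).

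**Assumptions:** script lengths, non-fill rates and the SD of PDC. The documents give none of these.

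**1. Score of a never-filler** = (script days − 0)/(30 − D). The true value is 0 in every row.

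| Script (assumed) | D | Recorded PDC |
|---|---|---|
| 24 days | 6 | 24/24 = 100% |
| 30 days | 6 | 30/24 = 125% |
| 30 days | 14 | 30/16 = 188% |
| 14 days | 7 | 14/23 = 61% |

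**2. Partial fill.** A participant fills and takes half of a 24-day script, with D = 6. Recorded: (24 − 0)/24 = 100%. True: 12/24 = 50%.

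**3. Effect on an arm mean, n = 45.** Each never-filler adds score/45: 100/45 = 2.2 points, 61/45 = 1.4, 125/45 = 2.8. With two never-fillers scored 100% and 43 fillers at 85%:
- true mean: 43 × 0.85/45 = 81.2%
- recorded mean: (43 × 0.85 + 2)/45 = 85.7%

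**4. Effect on the arm difference.** Let a share f never fill, with fillers at 85% and scripts that exactly cover the days due. The true mean is 0.85(1 − f) and the recorded mean is 0.85(1 − f) + f. For f = 5% that is 80.8% against 85.8%; for f = 10%, 76.5% against 86.5%. The bias in the difference is therefore the gap in non-fill shares, and equal non-filling gives none.

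**5. False non-inferiority.** Take a true difference of −15 points, 5 points more non-filling on apixaban, and never-fillers scored 100%. The recorded difference centres on −10 points. The probability of declaring non-inferiority is Φ(0.05/SE − 1.645), with SE = SD × √(2/45).

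| SD (assumed) | Basis | Probability |
|---|---|---|
| 0.25 | illustrative | 24.3% |
| 0.286 | 0.15 × √22.5/(1.645 + 0.842), implied by 45 per arm | 20.7% |
| 0.357 | √(0.85 × 0.15) | 16.3% |

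With no gap it is 5.0%.

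**6. Simulation** (40,000 trials, beta-distributed filler PDC, SD 0.25, enoxaparin fillers at 85%, apixaban fillers set to give the stated true difference):
- Non-fill 10% apixaban, 5% enoxaparin, true difference −15 points: non-inferiority is declared in about 25% of trials as written, and in about 5% if never-fillers score 0.
- Non-fill 5% apixaban, 10% enoxaparin, true difference 0: power is about 62% as written, and about 71% if never-fillers score 0.

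**7. Which way could it go?** Table 1 does not settle it. Copays above $50: 7/47 (15%) apixaban, 31/269 (12%) enoxaparin. Copays of $20 or less: 29/47 (62%) and 211/269 (78%). Section 2.2 cites compliance events of 0% with apixaban and 33.5% with enoxaparin, but that comparison was not randomized and the events are not non-fills.

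**The case against.** The governing definition concerns drug actually taken, under which a never-filler scores 0. The count is made live by phone, and a person with nothing to count would probably say so. Given or provided, in sections 9.3 and 3, could mean supplied. Section 6 says that poor compliance is tracked as the primary outcome, so the intent is clear. On this view the plan merely lacks a rule for non-fills. That does not rescue the text. Section 7.1 fixes the source as the prescription size in the medical record, and section 6 says the study supplies no drug. Someone who follows 9.3 records full credit. Someone who improvises may call the value missing, and 9.7 then discards it. Neither yields 0.

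Several limits on the consequences do stand:
- The documents give no non-fill rate, so the size of the bias is unknown.
- The 16–24% range reflects one assumed gap at one-sided 0.05. A 2-point gap gives 8–10%. At one-sided 0.025, the one-sided equivalent of the two-sided 0.05 in section 9.1, the 5-point gap gives 9.8–15.6%.
- Scores above 100% would probably prompt a query. The silent cases are scripts no longer than the days due, and partial fills.
- Section 9.4 defines adherent as having taken everything intended, so the safety-set consequence holds only if that status is derived from the count.
- The PMAS, the satisfaction items, out-of-pocket cost and COST-FACIT would still capture barriers. The masking is confined to analyses that use PDC.

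**Conclusion.** The concern holds. As written, the calculation gives a never-filler script days/(30 − discharge day) instead of 0, which is 100% or more whenever the script covers the days due. This follows from the text and needs no assumption about how many people fail to fill.

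The effect on the trial does rest on assumptions. Each never-filler scored 100% raises an arm mean by 2.2 points at 45 per arm. Equal non-filling inflates both means without biasing the difference. More non-filling on apixaban favours a false non-inferiority conclusion, and more on enoxaparin costs power. The documents do not establish which is likelier. Because the rule can record the worst adherence as the best on the sole primary endpoint, it should be corrected before PDC is collected and analysed.

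**What to change.** - In sections 7.1 and 9.3, define PDC = min(1, (units obtained − units remaining)/(units prescribed per day × days due)), and align the inputs listed in section 3. The units-per-day term only makes the conversion to days explicit.
- At the POD30 call, ask whether the prescription was filled and how much of it. Check the answer against the pharmacy records already reviewed for cost, where available.
- Score confirmed never-fillers as PDC = 0, and state in 9.7 that they are not missing data.
- Derive the binary adherent endpoint (9.4) and the adherent safety set (9.7) from the same quantity.
- Report never-fillers by arm.

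The cost is a few sentences in the sections named and one added question at the call. Average PDC may come out lower, and fills at outside pharmacies will rest on the participant's report. The question needs to be in place while calls are being made, because quantities obtained elsewhere may not be recoverable afterwards.
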